## 8.6 Data Monitoring Committee

There are no plans to include a Data Monitoring Committee for this study. Ensifentrine has demonstrated to have a safety profile similar to placebo in subjects with COPD.

# 9.0 STATISTICAL CONSIDERATIONS

Further details of the analyses to be performed can be found in the Statistical Analysis Plan (SAP).

## 9.1 Statistical Hypotheses

The aim of this study is to quantify both improvement CAT scores and responder proportions in subjects with moderate/severe COPD treated with ensifentrine (3 mg) for 12-weeks. No formal statistical tests will be performed. Study conclusions will be based on two-sided unadjusted 95% confidence intervals for estimated change and derived proportions.

## 9.2 Sample Size Determination

A sample size of approximately 20 subjects provides the ability to demonstrate a responder proportion estimate statistically differs from zero. Assuming a 30 percent response rate in the study population, 20 subjects provides the ability to demonstrate the derived proportion differs from zero determined by the lower two-sided 95% confidence limit derived from the estimated count using a normal approximation assuming a standard error equal to the square root of 6.

Twenty subjects also provides the ability to demonstrate the estimates of mean change from baseline does not extend to the clinically meaningful deterioration limit of (+2 units). Assuming estimated mean improvement of 1 unit with a corresponding standard deviation equal to 4.5, 20 subjects provides the ability to demonstrate the upper 95% confidence interval for a mean change from baseline estimate does not exceed 2 units.

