### Subjects

Approximately 20 subjects are planned to be enrolled in and complete this study.

Potential subjects will be included if the following criteria are met: aged 40 - 80 years with a clinical diagnosis of stable, moderate-to-severe COPD (forced expiratory volume in 1 second [FEV1]  $\geq$ 30% and  $\leq$ 75% of predicted normal); spirometry-confirmed airflow obstruction (pre- and post-bronchodilator FEV1/FVC <0.70), a score of  $\geq$ 10 on the CATTM; a score of  $\geq$ 2 on the mMRC; taking inhaled (but not nebulized) LAMA+LABA or LAMA+LABA+ICS (capped at 10 subjects) for at least 8 weeks, and are able to use the standard jet nebulizer correctly.

Potential subjects with asthma or other significant lung disease, recent hospitalizations, or serious infections; are pregnant or breastfeeding; or are unsuitable to participate, as judged by the Investigator, will be excluded.

Refer to the complete eligibility list in Section 5.0.

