# 5 Sample Size Justification

A sample size of approximately 20 subjects provides the ability to demonstrate a responder proportion estimate statistically differs from zero. Assuming a 30 percent response rate in the study population, 20 subjects would provide an expected count of 6 events. The two-sided 95% confidence interval for the number of events generated via normal approximation is (1.199, 10.801). Thus,20 subjects provide the ability to demonstrate the derived proportion differs from zero determined by the lower two-sided 95% confidence limit derived from the estimated count using a normal approximation assuming a standard error equal to the square root of 6.

Twenty subjects also provide the ability to demonstrate the estimates of mean change from baseline does not extend to the clinically meaningful deterioration limit of (+2 units). Assuming estimated mean improvement of 1 unit with a corresponding standard deviation equal to 4.5, 20 subjects provide the ability to demonstrate the upper 95% confidence interval for a mean change from baseline estimate does not exceed 2 units.

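### The sample-size text gives a binary endpoint a Poisson standard error, so the planning interval is too wide, and its 30% responder rate is hard to square with the planned mean change and SD

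*Protocol*

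**What the plan says.** Protocol 9.2 (repeated in the synopsis, 1.1) opens: "A sample size of approximately 20 subjects provides the ability to demonstrate a responder proportion estimate statistically differs from zero". The calculation begins "Assuming a 30 percent response rate in the study population" and takes a normal approximation to the responder count, "assuming a standard error equal to the square root of 6". SAP 5 adds the intermediate step, "20 subjects would provide an expected count of 6 events", and prints the result: "The two-sided 95% confidence interval for the number of events generated via normal approximation is (1.199, 10.801"). The only conclusion drawn is that the lower limit is above zero.

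The next paragraph of both documents plans the same 20 subjects for the mean change in CAT total score: "Assuming estimated mean improvement of 1 unit with a corresponding standard deviation equal to 4.5". It concludes that the upper 95% limit stays below a worsening of 2 units.

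A responder is a subject whose CAT total score improves by at least 2 from baseline; the primary time point is Week 12 (Protocol 3.2). Neither document gives a source for the 30%, the mean or the SD, links them to each other, or states a distribution for the change scores.

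**The concern.** There are two separate points.

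- **Variance.** The primary endpoint is yes or no per subject. The count among 20 independent subjects cannot exceed 20 and its variance is np(1 - p). The plan uses np, which is the variance of a Poisson count. At 30% the factor (1 - p) = 0.7 is not negligible.
- **Inputs.** The responder rate and the mean change describe the same score in the same subjects. Once the distribution of change is fixed, so is the share improving by 2 or more. The assumed 30% looks low for a mean improvement of 1 and SD 4.5.

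Protocol 9.1 says: "Study conclusions will be based on two-sided unadjusted 95% confidence intervals for estimated change and derived proportions". The planning interval is therefore the reader's only advance picture of how precisely the primary endpoint will be estimated. If the planning rate is also no higher than the rate expected with no average change, a reader should be told so before treating 30% as a favourable result.

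**Working it through.** **Inputs.** n = 20, responder rate 0.30, SE sqrt(6), mean improvement 1, SD 4.5 (Protocol 9.2); expected count 6 and interval 1.199 to 10.801 (SAP 5); cut-off of 2 or more (Protocol 3.2). Normality of change scores is my assumption.

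**1. Reproduce the plan's figures.**
- Count: 6 ± 1.96 x sqrt(6) = 6 ± 4.801 = 1.199 to 10.801, as printed. Divided by 20: 6.0% to 54.0%.
- Mean: -1 + 1.96 x 4.5/sqrt(20) = +0.97, or +1.11 with t on 19 df. Both are below +2, as stated.

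**2. Interval with the binomial variance.**
- SE = sqrt(20 x 0.3 x 0.7) = sqrt(4.2) = 2.049. Ratio: 2.449/2.049 = 1.195, so the plan's SE is about 20% too large.

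| Method, 6 of 20 | Count | Proportion |
|---|---|---|
| Plan, SE sqrt(6) | 1.20 to 10.80 | 6.0% to 54.0% |
| Normal approximation, binomial SE | 1.98 to 10.02 | 9.9% to 50.1% |
| Wilson | 2.9 to 10.4 | 14.5% to 51.9% |
| Exact (Clopper-Pearson) | 2.4 to 10.9 | 11.9% to 54.3% |

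**3. Responder rate implied by the mean and SD, if change is normal.** P(improvement ≥ c) = 1 - Phi((c - mean)/4.5), with c = 2, or c = 1.5 to allow for integer scores.
- Mean improvement 1: 1 - Phi(0.222) = 41.2%; 1 - Phi(0.111) = 45.6%.
- No mean change: 1 - Phi(0.444) = 32.8%; 1 - Phi(0.333) = 36.9%.
- Mean that gives 30% with SD 4.5: 2 - 0.524 x 4.5 = -0.36, or 1.5 - 2.36 = -0.86. That is an average worsening of 0.36 to 0.86 units.
- SD that gives 30% with mean improvement 1: (2 - 1)/0.524 = 1.91, or (1.5 - 1)/0.524 = 0.95. The plan has 4.5.

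**4. Does the stated conclusion survive?**
- At 41.2% the expected count is 8.24, with lower limit 2.6 (Poisson form) or 3.9 (binomial). At 45.6% it is 9.12, with lower limit 3.2 or 4.8.
- Every lower limit above, including those at 30%, exceeds zero.
- With n = 20 the normal-approximation lower limit first exceeds zero at 4 responders under either SE: 4 - 1.96 x 2 = 0.08, and 4 - 1.96 x sqrt(3.2) = 0.49.

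**The case against.** The best defence has four parts.

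- **The SE is disclosed and the arithmetic is right.** The plan says it takes a normal approximation to a count with SE sqrt(6), and the interval follows exactly. This stands: nothing is miscalculated from its stated inputs. Disclosure does not make the variance suitable for a binary outcome.
- **It matches the planned model.** Protocol 9.3.2 and SAP 8.4.5.2 analyse responders by negative binomial regression, which is a count model. That explains the choice. Whether a count model suits binary data is a question for the analysis section and is not settled here.
- **It is conservative, and the replacement is also approximate.** Both are true. At n = 20 and p = 0.3 the actual coverage is 96.4% for the sqrt(count) interval and 94.7% for the binomial normal approximation. The plan's upper limit of 54.0% happens to lie close to the exact 54.3%; its lower limit of 6.0% is well below the exact 11.9%. This is a reason to prefer an exact or Wilson interval.
- **The inputs can coexist without normality.** A shifted exponential with mean improvement 1 and SD 4.5 (skewness 2) gives 29.5% responders at cut-off 2. So would 30% of subjects improving by 7.87 and 70% worsening by 1.95. Such shapes are possible, but neither document suggests them, and the planned mixed model for the same score rests on normal theory.

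A reader might infer that the 30% contradicts the mean and SD. The documents do not support that: the conflict depends on a distribution they never state. A reader might also infer that the precision for the primary endpoint cannot be known. It can: SAP 5 prints the interval, and dividing by 20 gives 6% to 54%.

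**Conclusion.** The point holds in two parts of unequal certainty.

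- **Certain:** for a binary endpoint in independent subjects, the SE of the count at 30% of 20 is 2.05, not 2.45. The printed interval is too wide for a normal approximation: 6% to 54% against about 10% to 50%.
- **Conditional on roughly normal change scores:** mean improvement 1 with SD 4.5 implies 41% to 46% responders, and no mean change implies 33% to 37%. The 30% planning rate is then hard to reconcile with the other inputs and lies below the no-change rate.

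It would go too far to conclude that the sample-size figures are wrong or that 20 subjects is the wrong number. The figures follow from their stated inputs, the interval errs on the conservative side, and the lower limit exceeds zero under either SE at 30%, 41% or 46%. What changes is the description of precision and the meaning a reader can attach to a 30% rate.

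**What to change.** In Protocol 1.1 and 9.2 and in SAP 5:

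1. Replace sqrt(6) and (1.199, 10.801) with the binomial standard error (2.05 for the count) and a binomial interval, preferably exact (11.9% to 54.3%) or Wilson (14.5% to 51.9%). Note that SAP 8.4.5.2 uses a count model, so the reported interval may differ from the planning one.
2. Either align the 30% with the mean and SD (41% to 46% under normality), or keep it and say why it differs, for example as a deliberately cautious value or because skewed change is expected. Give the source of each input.
3. State the approximate no-change responder rate (33% to 37%) beside it, labelled as resting on normality and SD 4.5.

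The cost is wording in the two documents. N stays at 20, and the conclusion that the lower limit exceeds zero is kept. The justification will read less favourably once the no-change rate is shown.

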## 9.3 Statistical Methods

In general, unless stated otherwise, continuous variables will be summarized using descriptive statistics (number of subjects, mean, standard deviation [SD], median, minimum, and maximum values) and for categorical (nominal) variables, the number and percentage of subjects will be used.

In general, unless stated otherwise, continuous variables will be summarized using descriptive statistics (number of subjects, mean, standard deviation, median, minimum, and maximum values) and for categorical (nominal) variables, the number and percentage of subjects will be used.

## 9.3.1 **Populations for Analyses**

Allocation of subjects to the analysis populations (and whether any subjects or specific data from a subject will be excluded) will be determined prior to database lock.

The Full Analysis Set (FAS) will consist of all subjects that were administered the study medication at Visit 2 and have a CAT completed at baseline and from at least one post-treatment visit.

The Safety Analysis Set (SAS) will consist of all subjects who were administered the study medication at Visit 2.

## 9.3.2 Statistical Analyses

Continuous endpoints will be summarized as change from baseline using a mixed model for repeated measures with model terms for time and background therapy, and with baseline included as a covariate. Within subject error will be modeled using an unstructured covariance matrix, and Kenward-Roger method will be used to estimate degrees of freedom. Least square mean estimates, standard errors, and corresponding 95% confidence limits will be presented at each post-treatment time of assessment.

Response frequencies will be summarized by negative binomial regression with model terms for time and background therapy, and with baseline included as a covariate. Within subject correlation in responder status will be modeled using an unstructured covariance matrix. Response proportions, standard errors, and corresponding 95% confidence limits will be generated from estimated frequencies and presented for each post-treatment time of assessment.

## 9.3.3 Efficacy Analyses

Analysis will be based on the FAS.

Continuous variables will be summarized both for the absolute value and for change from baseline using descriptive statistics (N, mean, median, SD, minimum, and maximum), generated separately as well as overall.

Results will provide the number of subjects included in each analysis, estimated least square means and corresponding standard errors and 95% confidence intervals (CIs).

Total score data will be used for the change from baseline CAT analysis and the responder analysis.

Individual CAT item score (8-items) will be used for the change from baseline item-level analysis.

An analysis of the proportion of subjects with an improvement from baseline in CAT score of 2 or more will be summarized by visit and analyzed using negative binomial regression.

CAT total score and the individual item scores will be listed for each visit (items: Cough, Mucus, Chest Tight, Breathless, Limited Activities, Confident, Sleep and Energy). A plot of the least square means change from baseline in total score over time will be presented (based on the MMRM analysis).

Additional details will be provided in the SAP.

#### 9.3.4 Safety Analyses

Safety analysis will be descriptive and based on the SAS including all treated subjects.

AEs will be analyzed using quantitative and qualitative measures. Treatment emergent adverse events (TEAEs) will be summarized by treatment for all AEs, related AEs, SAEs, deaths, AEs leading to discontinuation of study medication or to withdrawal from study, AEs of different severity and AEs of different chronicity.

TEAEs will be coded using the Medical Dictionary for Regulatory Activities (MedDRA) and summarized by system organ class (SOC) and preferred term (PT) for each treatment. Adverse events will be included in subject listings. Seriousness, relatedness, and outcome will be identified in subject listings.

Vital signs will be summarized as change from baseline values for each parameter. Vital signs will be included in subject listings. Abnormal values and marked abnormalities will be identified in subject listings.

## 9.3.5 Other Analyses

Subject disposition including total number of screened subjects, number of completers, withdrawn subjects (including reason for withdrawal) and subjects included in each analysis set will be summarized overall. Subject disposition will be included in subject listings.

The number of subjects with major protocol deviations will be summarized by type and category of violation overall. Major protocol deviations will be included in subject listings.

Demographic and baseline characteristics will be summarized using descriptive statistics overall. Demographic and baseline characteristics will be included in subject listings.

Medical history will be coded using MedDRA and summarized by SOC and PT for each sequence and overall. Medical history will be provided in subject listings.

Prior medications will denote medications used prior to the first dose of study medication. Prior medications will be summarized and provided in subject listings. Prior medications will be provided in subject listings.

Concomitant medications will denote medications started prior to but continuing after receipt of study medication. Concomitant medications will be summarized separately by Anatomical Therapeutic Chemical (ATC) levels 2 and 4. Concomitant medications will be included in subject listings.

Compliance to study medication will be computed based on the number of ampules/foil pouch count dispensed and unused ampules/foil pouches returned. Non-compliance will

#### Protocol RPL554-CO-303

be defined as a compliance value less than 70% over the full study period. Compliance will be summarized overall.

## 9.3.6 Missing Data

As discontinuation of study medication will result in subject withdrawal, data collected after treatment withdrawal will not be included in the analyses, and missing data will not be imputed.

## 9.4 Interim Analyses

There will be no formal interim analysis in the study.

# Appendix 1 Abbreviations

AE	Adverse event	
ALT	Alanine aminotransferase	
ATS	American Thoracic Society	
BID	Twice daily	
CI	Confidence interval	
COPD	Chronic obstructive pulmonary disease	
CV	Coefficient of variation	
eCRF	Electronic case report form	
ERS	European Respiratory Society	
FAS	Full analysis set	
FDA	Food and Drug Administration	
FEV 1	Forced expiratory volume in 1 second	
FVC	Forced vital capacity	
GOLD	Global Initiative for Chronic Obstructive Lung Disease	
IB	Investigator's brochure	
ICF	Informed consent form	
ICS	Inhaled corticosteroid(s)	
IEC	Independent Ethics Committee	
IRB	Institutional Review Board	
LABA	Long-acting β2-agonist	
LAMA	Long-acting muscarinic antagonist	
LDPE	Low-density polyethylene	
MedDRA	Medical Dictionary for Regulatory Activities	
PDE	Phosphodiesterase	
PT	Preferred term	
QTcF	QT interval corrected for heart rate using Fridericia's formula	
SAE	Serious adverse event	
SAP	Statistical analysis plan	
SAS	Safety analysis set	
SD	Standard deviation	
SoA	Schedule of Activities	
SOC	System organ class	
SUSAR	Suspected unexpected serious adverse reaction	
TEAE	Treatment-emergent adverse event	
ULN	Upper limit of normal	
US	United States	
Verona	Verona Pharma plc.	
WOCBP	Women of Childbearing Potential	

# Appendix 2 Regulatory, Ethical, and Study Oversight Consideration

#### **Regulatory and Ethical Considerations**

- This study will be conducted in accordance with the protocol and with the following:
  - Consensus ethical principles derived from international guidelines including the Declaration of Helsinki and Council for International Organizations of Medical Sciences (CIOMS) International Ethical Guidelines.
  - Applicable International Council for Harmonisation (ICH) Good Clinical Practice (GCP) Guidelines.
  - Applicable laws and regulations.
- The protocol, protocol amendments, ICF, Investigator Brochure, and other relevant documents (e.g., advertisements) must be submitted to an IRB/IEC by the Investigator and reviewed and approved by the IRB/IEC before the study is initiated.
- Any amendments to the protocol will require IRB/IEC and regulatory authority approval, when applicable, before implementation of changes made to the study design, except for changes necessary to eliminate an immediate hazard to subjects.
- The Investigator will be responsible for the following:
  - Providing written summaries of the status of the study to the IRB/IEC annually or more frequently in accordance with the requirements, policies, and procedures established by the IRB/IEC.
  - Notifying the IRB/IEC of SAEs or other significant safety findings as required by IRB/IEC procedures.
  - Providing oversight of the conduct of the study at the study center and adherence to requirements of 21 Code of Federal Regulations (CFR), ICH guidelines, the IRB/IEC, EU Clinical Trials Directive 2001/20/EC (if applicable), and all other applicable local regulations.
- After reading the protocol, the Principal Investigator will sign the protocol signature page and send a copy of the signed page to the Sponsor or designee. The study will not start at any study center at which the Investigator has not signed the protocol.

#### Adequate Resources

The Investigator is responsible for supervising any individual or party to whom the Investigator delegates study-related duties and functions conducted at the study center.

If the Investigator/institution retains the services of any individual or party to perform study related duties and functions, the Investigator/institution should ensure this individual, or party is

#### Protocol RPL554-CO-303

qualified to perform those study-related duties and functions and should implement procedures to ensure the integrity of the study-related duties and functions performed and any data generated.

#### **Financial Disclosure**

Investigators and sub-Investigators will provide the Sponsor with sufficient, accurate financial information as requested to allow the Sponsor to submit complete and accurate financial certification or disclosure statements to the appropriate regulatory authorities. Investigators are responsible for providing information on financial interests during the course of the study and for 1 year after completion of the study.

#### Insurance

Financial arrangements are detailed in the Investigator Agreement between the Sponsor and Investigator.

The Sponsor will arrange clinical study insurance to compensate subjects for any potential injury or death caused by the study.

#### **Informed Consent Process**

- The Investigator or his/her representative will explain the nature of the study to the subject and/or the subject's legally authorized representative and answer all questions regarding the study.
- Subjects must be informed that their participation is voluntary. Subjects will be required to sign a statement of informed consent that meets the requirements of 21 CFR 50, local regulations, ICH guidelines, Health Insurance Portability and Accountability Act (HIPAA) requirements, where applicable, and the IRB/IEC or study center.
- The medical record must include a statement that written informed consent was obtained before the subject was entered in the study and the date the written consent was obtained. The authorized person obtaining the informed consent must also sign the ICF.
- A copy of the original ICF(s) must be provided to the subject or the subject's legally authorized representative.
- ICF New Information: New information since the time of the original consent can be presented to subjects in format(s) or method(s) including, but not limited to those listed below unless excluded by local requirements:
  - Revised consent document
  - Addendum to consent
  - Memo or other communication to subjects
  - Orally by phone or in person

#### Version 4.0; 19 August 2024

#### Protocol RPL554-CO-303

Documentation of the method the new information was presented to the subject along with the name of the site staff member and date the new information was presented to the subject must be documented in the subject's source document.

